1.1.1 Preclinical Pharmacology

During the development of SB204 (berdazimer sodium gel co-administered with hydrogel) for acne, SB206 (berdazimer sodium gel co-administered with hydrogel) for the treatment of external genital warts and perianal warts, SB208 (berdazimer sodium gel co-administered with hydrogel) for tinea pedis and SB414 (berdazimer sodium ointment co-administered with hydrogel), Novan has conducted over 90 nonclinical studies. In addition, specifically for SB206, Novan completed a 4-week daily dosing with 2-week recovery GLP dermal bridging study in miniature swine. Under the conditions of this study, the No Observed Adverse Effect Level (NOAEL) was considered to be greater than the nominal dose level evaluated (~48 mg/kg/day berdazimer sodium which equates to approximately 1.7 mg/cm²/day), administered as BID 8% SB206 Gel or QD 12% SB206 Gel. There were no meaningful effects on mortality/moribundity, clinical observations, physical examination findings, food consumption, weekly body weight or weekly body weight change, clinical pathology parameters, ophthalmologic or electrocardiographic examinations, or organ weight findings. Microscopic changes, limited to the superficial dermis and epidermis, were minimal to mild but had not completely resolved following the 2-week recovery period. The induced changes included hyperkeratosis, epidermal hyperplasia and mononuclear dermal inflammation (mononuclear cell infiltration and dermal edema). Due to an insufficient number of plasma samples with quantifiable hydrolyzed n-methylaminopropyl-trimethoxysilane (hMAP3)

concentrations (values above the LOQ of 5 ng/mL), it was not possible to perform a noncompartmental TK analysis. There was no evidence of systemic nitric oxide exposure at any of the dose levels tested. This study with SB206 in miniature swine was successful in bridging the safety of topical administration of berdazimer sodium in the SB204 formulation with the SB206 formulation.

For additional information refer to the Investigator's Brochure (IB).

1.1.2 *Pharmacokinetics*

The systemic bioavailability of berdazimer sodium after dermal administration has been investigated in two maximal use studies in adults and adolescent subjects with moderate to severe acne vulgaris, and no quantifiable systemic exposure was observed. In adult subjects with moderate to severe acne vulgaris (NI-AC101) administration of SB204 8% (berdazimer sodium gel 16% co-administered with hydrogel) or Vehicle Gel daily for 5 days to the face, chest, back, upper shoulders twice daily (BID) (17% body surface area [BSA]) showed no detectable systemic exposure on Day 1 or Day 5 to hydrolyzed N-methylaminopropyl-trimethoxysilane (hMAP3), a silicon containing component of the parent compound. There was no noticeable difference in systemic nitrate levels on Day 1 or Day 5 in subjects treated with SB204 or Vehicle Gel and no evidence of accumulation. Likewise, in an open-label pharmacokinetic (PK), study (NI-AC103) in adolescents (ages 9-16 years) with moderate to severe acne vulgaris topical administration of SB204 4% was applied once daily (QD) for 21 days to 17% BSA and again no detectable systemic exposure to hMAP3 and no plasma nitrate concentrations outside of normal variability and negligible accumulation of nitrate after 21 days of dosing.

Additionally, in a 4-way, randomized, double-blind, cross-over study examining electrocardiogram (ECG) effects following SB204 application (NI-AC104), there was no quantifiable systemic exposure to hMAP3 and no difference in plasma nitrate levels in 48 subjects with moderate to severe acne treated with SB204 (berdazimer sodium) 4%, SB204 (berdazimer sodium) 12% or Vehicle Gel applied to 17% BSA. No changes in ECG were observed with therapeutic or supratherapeutic doses of SB204.

In a 2-week atopic dermatitis (AD) study (NI-AD101), and a 4-week psoriasis (NI-PS101) study, a limited number of subjects who received SB414 6% (berdazimer sodium ointment 12% co-administered with buffered hydrogel) demonstrated quantifiable systemic exposure to the study treatment at limited time points. Although both SB206 and SB414 have the same active pharmaceutical ingredient, the formulations are different: SB206 is a gel and SB414 is a cream. The cream formulation of SB414 resulted in low and not quantifiable systemic exposure to hMAP3 observed in the NI-AD101 and NI-PS101 studies for all but 2 subjects at 12 hours post-dose. Note that SB414 formulation is cream while SB204 formulation is gel, similar to SB206.

In the NI-MC201 study, plasma hMAPs concentrations in all PK blood samples at Week 12 or end of treatment were below the lower limit of quantitation (LLOQ).

1.1.3 Potential for Drug-Drug Interactions

Since no quantifiable exposure has been observed to date with SB204 and SB206 clinically, the risk of drug-drug interactions is low.

1.1.4 Clinical Adverse Event Profile

As of December 31, 2018, topical formulations of berdazimer sodium at concentrations ranging from 1% to 16% have been studied in 21 completed studies. Almost 1600 healthy volunteers or subjects with acne, genital warts, tinea pedis, psoriasis and atopic dermatitis have been exposed to Vehicle and over 2700 exposed to berdazimer sodium.

Novan completed a Phase 2 ascending dose study of SB206 in 256 subjects with MC. No deaths or serious adverse events (SAEs) occurred during this study. Seven subjects were discontinued from treatment with the study drug due to an AE, all in active treatment groups (3 subjects in the 4% BID group; 2 in the 8% BID group; and 2 in the 12% BID group). Treatment discontinuation was due to application site reactions in 6 of these subjects and to worsening MC in the other. The active study drug (SB206) given at doses ranging from 4% BID to 12% QD was well tolerated. Most AEs were mild to moderate. The only AEs that appeared to be clearly associated with SB206 were those involving administration site reactions.

Novan completed a Phase 2 ascending dose study assessing the tolerability, safety, and efficacy of SB206 in subjects with external genital warts (EGW) and perianal warts (PAW). In this study, there were no safety concerns with single daily dose application; BID application of SB206 to the genitalia was associated with local application site reactions in some subjects which led to treatment discontinuation. The results of this study are supportive of the continued clinical development of SB206.

SB204 is in development for the treatment of acne vulgaris. The acne clinical program for SB204 includes 9 completed Phase 1 studies in healthy volunteers or subjects with acne vulgaris, 3 completed Phase 2 studies, and the completed Phase 3 program (two 12-week placebo-controlled studies and one 40-week open label long-term safety study in subjects ages 9 years old and older). Based on the clinical data acquired to date, topical application of berdazimer sodium to healthy volunteers or subjects with acne vulgaris has generally been well-tolerated with no safety concerns identified.

Novan has also completed a study in subjects with tinea pedis using SB208. There were no safety concerns identified with QD dosing to one or both feet; there were no application site AEs reported.

Novan has completed two studies in subjects with atopic dermatitis and psoriasis using SB414. In both studies, SB414 was generally well tolerated and the incidence of treatment-related treatment-emergent adverse events (TEAEs) was low. Administration site reactions were the most common treatment-related adverse events and tolerability (change in itch and burning/stinging) was similar across treatment groups. There was no evidence of meaningful trends in safety parameters. In completed studies, no clinically significant changes have been observed in laboratory assessments in subjects treated with topical berdazimer sodium. There have been no clinically significant changes in physical examination, including vital signs, in subjects treated with topical berdazimer sodium.

1.1.5 *Elevations in Liver Function Tests*

No clinically significant changes have been observed in laboratory assessments.

1.1.6 *Potential Risk of Testicular Injury*

In a nonclinical GLP study of fertility and early embryonic development in rats after daily oral administration of berdazimer sodium there was no adverse findings in male fertility parameters or reproductive parameters in either sex.

Additionally, since no quantifiable exposure has been observed to date after dermal administration of SB204 and SB206 clinically, the risk of testicular injury is low.

1.1.7 *Potential Risk to Fetal Development*

Oral administration of berdazimer sodium drug substance in GLP embryo-fetal developmental toxicity studies in rats and rabbits showed minor effects on fetal development only at the highest doses.

Additionally, due to the lack of systemic exposure after dermal administration of SB204 clinically and SB206 clinically observed to date, the risk to fetal development is low.

In prior studies using berdazimer sodium in different diseases, there have been 6 reported pregnancies; of those, two were completed to term with healthy babies. One woman had an elective termination of her pregnancy and one woman had a miscarriage. The outcome of the other two pregnancies is unknown.

1.2 *Study Rationale*

MC is benign and generally self-limiting. The average duration of a single lesion is about 2 months; however, since the lesions spread easily by autoinoculation from scratching or trauma, the mean duration of infection is often more than a year.

Nitric oxide, an endogenous small molecule, provides localized immunity against foreign organisms by acting both as a short-lived immune modulator and a direct broad-spectrum antimicrobial agent. Topical exogenous nitric oxide has been investigated as an antimicrobial agent due to its broad-spectrum activity, ability to inhibit viral replication, and the ability to readily diffuse through cell membranes.

There is a significant unmet medical need to treat MC, considering most patients with MC are healthy young children. Ablative treatment often causes fear to the children and interferes in physician-patient relationships. Repeated ablative treatments are difficult. Using anesthesia involves safety risk and costs. Not treating increases the potential of further dissemination of the disease. Prevention of further dissemination of the disease is also important from a public health perspective. Topical application of SB206 may accelerate resolution of MC without causing pain and/or scarring, decrease the frequency of ablative treatment, and provide an effective, convenient treatment option for patients with MC.

1.2.1 *Dosing Regimen*

Subjects will apply treatment once daily to all lesions identified at Baseline and new lesions that arise during treatment for a minimum of 4 weeks and up to 12 weeks. Each dose of SB206 will consist of hydrogel thoroughly mixed with berdazimer sodium gel. Each dose of vehicle will consist of hydrogel thoroughly mixed with vehicle gel. Subjects will be instructed on the correct use of study drug and the amount to apply during Baseline/Day 1 according to the corresponding subject instructions for use that will be provided to the subject. In addition, study personnel will ensure that the subjects or caregivers can identify the treatment area(s) and know where and how to apply the study drug. Dosing should be applied at home, except on the day of study visits when the dose should be applied in the clinic. The subject, caregiver, or study personnel will apply to the lesions and approximately 1 cm surrounding each lesion. Periocular lesions will be treated if the lesions are at least 2 cm from the edge of the eye.

If the investigator determines all lesions are cleared at a clinic visit, the treatment may stop. At Weeks 2, 4, and 8, the investigator will determine if new lesions have occurred since the last visit, and the subject or caregiver will be instructed by the investigator to re-initiate treatment. If treatment is stopped due to clearance, subjects will continue regularly scheduled visits through Week 24/ET2. Subjects will be followed for recurrence/new lesions until Week 24. For the purpose of this study, a recurrence of MC will be documented as an AE.

1.2.2 *Dose Selection Rationale*

Novan completed a Phase 2 ascending dose study of SB206 in 256 subjects with MC. The primary endpoint for Study NI-MC201 was the proportion of subjects in the modified intent-to-treat population who achieved complete clearance of all MC lesions at Week 12. In this analysis, 8%

BID and 12% QD groups of SB206 were statistically significantly superior to vehicle in the proportion of subjects with complete clearance at Week 12: 20.0% (vehicle BID/QD combined), 41.0% (8% BID: $p=0.028$), and 41.9% (12% QD: $p=0.024$). The difference in proportion (95% CI) from vehicle was statistically significant for 8% BID (0.206 [0.022, 0.389], $P = 0.028$) and 12% QD (0.204 [0.027, 0.381], $P = 0.024$). A sensitivity analysis of the primary efficacy endpoint in the ITT population produced results consistent with the primary analysis results. Secondary and exploratory efficacy endpoints also support selection of 12% QD. In the Phase 2 study, 7 subjects were discontinued from treatment with the study drug due to an AE, all in active treatment groups (3 subjects in the 4% BID group; 2 in the 8% BID group; and 2 in the 12% BID group). Treatment discontinuation was due to application site reactions in 6 of these subjects and to worsening MC in the other. No subject discontinued treatment due to AEs in the 12% QD group.

Based on totality of the data, SB206 12% QD was selected for this Phase 3 study.

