Subjects will visit the clinic at Screening/Baseline, Week 2, Week 4, Week 8, Week 12, and Week 24. Subjects will be contacted via phone on Day 2 to collect subject information on early dose reactions. At Weeks 16 and 20, subjects will be contacted via phone to capture information regarding MC recurrence and AEs; at Week 24, the subject will be seen at the site for a final study visit. Subjects who discontinue the study prior to the Week 12 visit due to adverse events or other reasons will be asked to complete the Week 12 visit assessments; this will be recorded as an Early Termination (ET1) visit. No study drug treatment will be provided after the Week 12 visit. Subjects who discontinue from the study after Week 12 but prior to Week 24 will be asked to come to the site to complete Week 24 assessments; this visit will be recorded as an ET2 visit.

Safety assessments include BOTE Inflammation Scores, Local Skin Reaction Scores (LSRs), adverse event collection, including scarring/keloid and urine pregnancy tests (UPTs). Safety assessments will be completed at specified site visits through Week 12. After Week 12, safety information for ongoing AEs and new AEs will be collected, along with information regarding MC recurrence. For the purpose of this study, a recurrence of MC will be documented as an AE.

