If a subject's treatment is discontinued by the investigator or the subject because of an AE, that AE should be indicated as the reason for treatment discontinuation. All subjects will be encouraged to remain in the study throughout the 24-week study duration.

In the event of suspected allergic contact dermatitis, photographs may be taken of the affected area(s) and transmitted to the CRO medical monitor for review prior to initiating patch testing.

When approximately 200 subjects (cumulative across studies NI-MC302 and NI-MC302) have completed 4 weeks of treatment, a Data Safety Monitoring Board (DSMB) will review all available unblinded safety data (including completed patch testing results).

Table 1: Schedule of Assessments

	Screening	Treatment					
	Screening ¹ (Day -14 to Day 1)	Visit 1 ¹ Baseline (Day 1)	V2 Telephone Contact (Day 2)	Visit 3 ² Week 2 (Day 15 ±3)	Visit 4 ² Week 4 (Day 29 ±5)	Visit 5 ² Week 8 (Day 57 ±5)	Visit 6 ² Week 12/ ET1 (Day 85 ±5)
Informed Consent (Assent)	X						
Demographics	X						
Medical and Medication History	X						
Lesion Count or Recurrence	X	X		X	X	X	X
Physical Exam		X					X
Urine Pregnancy Test ³	X	X			X	X	X
BOTE Inflammation Score ⁴		X (pre-dose)		X	X	X	X
Local Skin Reactions (LSR) (post-dose) ⁴		X		X	X	X	X
Scarring/Keloid Assessment					X	X	X
DLQI/CDLQI ⁵		X					X
Review of Inclusion/Exclusion Criteria	X	X					
Drug Dispensed		X			X	X	
Dispense Subject Diary		X		X	X	X	
Review Subject Application Instructions		X		X	X	X	
In Clinic Study Drug Application ⁶		X		X	X	X	X
Review Study Drug Compliance				X	X	X	X
Collect Study Drug					X	X	X
Collect Subject Diary				X	X	X	X
Record Adverse Event (AE) and Concomitant Medication (CM) Changes ⁷		X	X	X	X	X	X

	Safety Follow-up		
	Visit 7 ² Week 16 Telephone Contact (Day 113±5)	Visit 8 ² Week 20 Telephone Contact (Day 141±5)	Visit 9 ² Week 24/ ET2 (Day 169±5)
Scarring/Keloid Assessment			X
Record Adverse Event (AE) and Concomitant Medication (CM) Changes ⁷	X	X	X

¹Screening and Baseline may occur on the same day. If this occurs, lesion count and review of inclusion/exclusion criteria will only occur once. If two members of the same household qualify for study participation, they must be randomized on the same day.

²All visit dates are in reference to Baseline, e.g. Week 2 occurs 14 days after Baseline Visit.

³Females 9 years of age and older.

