6.2.6 Visit 5/Week 8 (Day 57 ±5)

The following procedures must be performed and recorded at the Week 8 visit.

1. Obtain pregnancy test and evaluate results, as applicable. If pregnancy test is positive, the subject may continue in the study; however, study drug should be discontinued.
2. Perform lesion mapping and update lesion map with location for any new lesions.
3. Perform scarring/keloid assessment.
4. Weigh returned study drug and review study compliance.
5. Weigh, record, and dispense new supply of study product and dispense subject diary.

6. Review dosing instructions and have subject/caregiver apply daily dose in clinic using the newly dispensed kit.
7. Perform BOTE Inflammation Score (post-dose).
8. Perform Local Skin Reaction Assessment (post-dose).
9. Collect and record AE information for AEs reported.
10. Update concomitant medication information and confirm if any new occurrences of MC were reported in the subject's household.

6.2.7 *Visit 6/Week 12/ET (Day 85 ±5)*

The following procedures must be performed and recorded at the Week 12/ET1 visit.

1. Complete age-matched Dermatology Life Quality Index (DLQI) assessment, as applicable.
2. Obtain pregnancy test and evaluate results, as applicable.
3. Perform lesion mapping and update lesion map with location for any new lesions.
4. Perform scarring/keloid assessment
5. Perform a brief physical examination.
6. Subject/caregiver administer final dose of study drug from previously dispensed kit.
7. Perform BOTE Inflammation Score (post-dose).
8. Perform Local Skin Reaction Assessment (post-dose).
9. Weigh returned study drug and review study compliance.
10. Collect and record AE information for AEs reported.
11. Update concomitant medication information and confirm if any new occurrences of MC were reported in the subject's household.

6.2.8 *Visit 7/Week 16 and Visit 8/Week 20 (Day 113 +/- 7 days; Day 141 +/- 7 days)*

The following procedures must be performed and recorded at the Week 16 and Week 20 visits. It is expected that these visits should be done by telephone.

1. Collect and record information for new and ongoing AEs, including recurrence of MC.
2. Update concomitant medication information.

6.2.9 *Visit 9/Week 24 (Day 169 +/- 7 days)*

The following procedures must be performed and recorded at the Week 24 visit.

1. Perform scarring/keloid assessment.
2. Collect and record information for new and ongoing AEs, including subject recurrence of MC.

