7.1 Efficacy Assessments

7.1.1 *Molluscum Contagiosum Lesion Counts*

Molluscum contagiosum is a viral infection characterized by small, discrete, waxy, skin-colored, dome-shaped papules, an average of 3–5 mm in diameter. The papules may be umbilicated and contain a caseous plug. When the lesions are squeezed or traumatized, a creamy, grey-white material can be extruded. If the investigator cannot clearly differentiate the lesions as is the case for agminated (clustered lesions) this should be counted as one lesion. If the investigator can differentiate and count the umbilical tops separately, each lesion should be counted separately. The

investigator should be consistent with the method of recording agminated lesions throughout the study.

For the purpose of this clinical trial, only active MC lesions are counted. Treatable lesions are any active (raised, palpable) MC lesions that are dome-shaped, pearly and shiny white top centered papules that are at least 2 cm away from the ocular region.

All study personnel who will perform lesion counts must pass the study training including lesion count training. Training on how to accurately count the number of MC lesions will be provided.

Mapping of lesions: At every visit from Baseline through Week 12, all lesions should be recorded on the body map and will clearly note the location of each lesion or agminated lesion. The lesion map is intended to assist study personnel in performing lesion counting and scar/keloid assessment.

Definition of Clearance: For the purpose of this study, “clear” means resolution of the active (raised, palpable) treatable molluscum lesion(s). After resolution, the residual surface changes such as pitted scar (indentation) < 1 mm in depth at the molluscum lesion area (<5 mm in diameter), hyper or hypopigmentation may remain. As these are considered part of the normal healing, they will not be captured as adverse events. Refer to the lesion count training for details.

The same evaluator should perform lesion counts at Screening, Baseline, and Weeks 2, 4, 8 and 12/ET1. In the event that this is not possible due to unforeseen circumstances, a different evaluator may evaluate the subject. The evaluator must pass the study training including lesion count training. It is particularly important to ensure the same evaluator performs the Baseline and Week 12/ET1 for lesion count for a subject and also Baseline and Week 24/ET2 assessment for scarring/keloid scarring.

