4. STUDY DESIGN AND PLAN

This is a Phase 3 multi-center, randomized, double-blind, vehicle-controlled, parallel group study to be conducted in approximately 340 subjects ≥ 6 months of age with MC. After obtaining informed consent/assent, subjects who satisfy entry criteria will be randomized to a 2:1 (active:vehicle) scheme. Subjects receiving current treatment for MC at the time of the Screening Visit will enter a washout period of up to 14 days prior to randomization. In the event no washout period is required, Screening and Baseline visit activities may be combined into a single visit. At randomization, subjects will be stratified into 4 strata corresponding to the cross-classification of household number of randomly assigned subjects (1 subject per household vs 2 subjects per household) and investigator type (dermatologist vs other). Households randomizing 2 subjects will receive the same treatment assignment for both subjects. Up to 2 subjects from the same household may be randomly assigned on the same day, if both individually meet all inclusion and exclusion criteria. For subjects in the same household, Screening can occur on different days; however, the baseline visit must occur on the same day.

Subjects or their caregivers will apply SB206 12% or Vehicle Gel QD for a minimum of 4 weeks and up to 12 weeks to all lesions identified at Baseline and new treatable lesions that arise during the course of the study. Subjects or their caregivers will continue to treat the area until the next scheduled visit even if the lesion(s) clear. If the investigator determines all lesions are cleared at a clinic visit, the treatment may stop. At Weeks 2, 4, 8 and 12, the investigator will count and record the number of active (raised, treatable) molluscum lesions per body area. At Weeks 2, 4,

and 8, the investigator will determine if new lesions have occurred since the last visit, and the subject or caregiver will be instructed by the investigator to re-initiate treatment. If treatment is stopped due to clearance, subjects will continue regularly scheduled visits through Week 24.

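### MC recurrence is followed to Week 24, but the SAP defines the recurrence endpoint by lesion counts, which are clearly scheduled only to Week 12

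*Combined protocol and SAP*

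**What the plan says.** SAP references are to the last of the three versions in the file. All three share the recurrence definition and the AE window.

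**Follow-up.** Protocol section 1.2.1 says "Subjects will be followed for recurrence/new lesions until Week 24" and then "For the purpose of this study, a recurrence of MC will be documented as an AE". Section 4.1 adds: "After Week 12, safety information for ongoing AEs and new AEs will be collected, along with information regarding MC recurrence". The protocol synopsis and SAP section 4 name MC recurrence next to AEs as a subject of the Week 16 and 20 calls, and as one purpose of the Week 24 clinic visit.

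**Procedures after Week 12.** For the calls, protocol section 6.2.8 lists "Collect and record information for new and ongoing AEs, including recurrence of MC". For Week 24, section 6.2.9 lists "Collect and record information for new and ongoing AEs, including subject recurrence of MC". Neither lists a lesion count.

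**Lesion counts.** The Table 1 row "Lesion Count or Recurrence" stands in the screening and treatment part and is absent from the follow-up part. Protocol section 7.1.1 says "The same evaluator should perform lesion counts at Screening, Baseline, and Weeks 2, 4, 8 and 12/ET1". SAP section 4 says "At Weeks 2, 4, 8 and 12, the investigator will count and record the number of active (raised, treatable) molluscum lesions".

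**Analysis.** SAP section 10.1 makes the exploratory recurrence endpoint a total lesion count above 0 at any time once a 0 has been recorded. Section 11.3 gives it no method or denominator. Appendix D has one table for it, 14.2.3.5. Section 13.1 limits every AE summary to treatment-emergent events, and that window closes at the last application; no drug is provided after the Week 12 visit. Section 6 says the follow-up data will be analysed after the Week 24 lock, without naming a recurrence analysis.

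**The concern.** The recurrence endpoint in protocol section 3.3 carries no Week 12 limit, and half of the trial's calendar is spent asking about recurrence. Yet the SAP ties the endpoint to a measurement that the visit schedule stops making at Week 12. A relapse reported at Week 16, 20 or 24 as the protocol intends would not satisfy the SAP definition. SAP section 14, which lists changes from the protocol, does not mention this narrowing. In the same SAP list, scarring runs to Week 24 and household spread to Weeks 16, 20 and 24.

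At stake is the description of how durable clearance is. The protocol rationale describes a disease that spreads by autoinoculation and often lasts more than a year. A rate built on counts to Week 12 describes something different from a rate to Week 24, and the table title does not say which it is. Timing also matters. The blind is broken at the Week 12 freeze, and SAP section 6 labels any analysis devised after that as post hoc. A Week 24 recurrence rate has to be defined before the freeze to count as pre-specified.

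**Working it through.** The plan states no figure for recurrence, so the check sets the schedule against the definition and then sizes the affected group.

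**1. What each visit supplies**

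| Visit | Scheduled lesion count | Recurrence information | Can meet the SAP 10.1 definition |
|---|---|---|---|
| Weeks 2, 4, 8, 12 | yes | count | yes, if a 0 came earlier |
| Weeks 16, 20 (telephone) | no | report, within AE collection | no |
| Week 24 (clinic) | not in section 6.2.9, Table 1 or section 7.1.1 | report, within AE collection | no, unless a count is taken |

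A subject whose first 0 is at Week 12 has no later scheduled count and so cannot enter the numerator from scheduled data.

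**2. Time covered.** Visit days are from Table 1: Baseline Day 1, Week 12 Day 85, Week 24 Day 169.
- Total: 169 − 1 = 168 days.
- To the last scheduled count: 85 − 1 = 84 days.
- After it: 169 − 85 = 84 days, half of the total.

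For a subject first clear at Week w, the share of the time to Week 24 that scheduled counts can see is (12 − w)/(24 − w):
- w = 2: 10/22 = 45%
- w = 4: 8/20 = 40%
- w = 8: 4/16 = 25%
- w = 12: 0/12 = 0%

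These are shares of calendar time, not of events.

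**3. Subjects affected.** SAP section 5 plans 227 subjects on SB206 and 113 on vehicle, with a vehicle rate of 18% and a difference of 18 points, hence 36% on SB206. A two-proportion calculation with pooled variance on these inputs gives 94.4% power against the stated 94%, so the inputs are read correctly. Expected clear at Week 12:
- SB206: 0.36 × 227 = 81.7
- Vehicle: 0.18 × 113 = 20.3
- Total: about 102

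No clearly scheduled count can record a later recurrence in any of them. Any who had already cleared, relapsed and cleared again by Week 12 would be in the numerator from the earlier relapse.

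**4. Events affected, for illustration.** The relapse rate after Week 12 is not in the documents. With an assumed rate r, the same in both arms, the expected number is r × 81.7 + r × 20.3:

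| r (assumed) | SB206 | Vehicle | Total |
|---|---|---|---|
| 5% | 4.1 | 1.0 | 5.1 |
| 10% | 8.2 | 2.0 | 10.2 |
| 30% | 24.5 | 6.1 | 30.6 |

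**5. The AE route.** A recurrence AE with onset after Week 12 falls after the last application, so it is outside the treatment-emergent window and outside the AE tables in Appendix D. It would appear in Listing 16.2.7.1 (all AEs) and possibly in Listing 16.2.9.5 (telephone contacts).

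**The case against.** The best answer is that the plan is ambiguous about Week 24 rather than silent. SAP section 4 holds the Week 24 visit partly to assess recurrence, and its scar paragraph, which covers Week 24, has a sentence about counting active lesions. The definition has no Week 12 cut-off, so a Week 24 count, or one from an unscheduled visit, would enter Table 14.2.3.5. The eCRF and the table shells, which could settle whether a count or a recurrence field exists and what the table shows, are not in the documents. The protocol endpoint states no time horizon, and the period after Week 12 is labelled safety follow-up. The endpoint is exploratory, outside the testing hierarchy, with no between-arm test specified. Household spread reached Week 24 because that endpoint had a visit list to extend; recurrence never had one.

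Much of this stands, and it rules out two stronger readings. A reader might infer that recurrence after Week 12 is recorded only as an AE. The documents do not establish that, because the calls and the Week 24 visit name recurrence separately and a telephone listing is planned. A reader might also infer that no planned summary could contain these events. That cannot be asserted with the shells unseen, a Week 24 count not excluded, and a rule in SAP section 13.1 that treats an AE as treatment-emergent when a partial onset date leaves its timing undetermined.

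The definition itself is not rescued. It accepts a count and nothing else. The Week 24 procedure list, Table 1 and protocol section 7.1.1 agree in listing no count after Week 12, and no reading supplies one at the Week 16 and 20 calls.

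**Conclusion.** The point holds as a mismatch between an exploratory endpoint's definition and the data the protocol collects for it. Followed as written, the definition leaves out recurrences reported after Week 12, apart from unscheduled counts or a Week 24 count that is not clearly scheduled. About 102 subjects, 82 on SB206 and 20 on vehicle, would be exposed to this at the planned response rates. The number of relapses is unknown; the 5% to 30% range is illustrative only.

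The data are not lost, since they remain in subject listings. Nothing here bears on the primary or secondary tests, the sample size or the treatment-emergent AE totals, and no direction of bias between arms is claimed. This is a low-cost improvement to make before unblinding, not a threat to the trial's main conclusions.

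**What to change.** Before the Week 12 unblinding, revise SAP sections 10.1 and 11.3:

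- **Population:** subjects with at least one lesion count of 0. This supplies the missing denominator and keeps out new-lesion reports from subjects who never cleared.
- **Event:** the earlier of a later count above 0 or a report of MC recurrence (AE, telephone or clinic) with onset after that 0 count, through Week 24.
- **Table 14.2.3.5:** by arm, to Week 12 and after Week 12, by source, with the number of cleared subjects followed to Week 24.

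Leave the treatment-emergent AE tables as they are.

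The cost is one definition and one revised table, from data already collected. The downside is that telephone reports are less certain than a clinic count, which is why the source must be shown. A lesion count at the existing Week 24 visit would give firmer data, but it needs a protocol amendment; it is optional and the fix does not depend on it.
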